5.3.1 NCORP site

5.3.2 Most recent IRB approval date (either initial or annual-not an amendment date)

5.3.3 Name and telephone number of coordinator following the study participant

5.3.4 Treating component or subcomponent CTEP institution code

5.3.4.1 Enrolling physician CTEP Investigator ID

5.3.5 Confirmation that participant meets all inclusion/exclusion criteria requirements listed in Section 4.0 including

5.3.5.1 Documentation of eligibility screening score of  $\geq 10$  on the Insomnia Severity Index Screening Form.

5.3.5.2 Documentation of meeting DSM-V Insomnia diagnosis criteria on the DSM-V Screening Form.

5.3.5.3 Documentation of meeting all eligibility requirements on the Eligibility Checklist.

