5.3.7.8 Stratification: ISI severity screening score and current hormone therapy status (yes/no)

5.4 An email confirmation of registration will be sent from the URCC NCORP Research Base.

5.5 Registration and randomization of participants will occur when an entire cohort has been consented. A cohort consists of a yoga group, a CBT-I group and a health education group at a single NCORP location. All participants are registered at the same time. The minimum number of participants to comprise a cohort is 15 and the maximum is 30. The NCORP must notify the URCC when the final participant in a cohort is being consented, and provide the total number of participants enrolled to that cohort, the institution's CTEP ID, and the date of the first day of the baseline week. The Research Base requires a 24-hour turn-around time to open the registration site. The NCORP site must then register the entire cohort of participants within 24 hours and will receive the randomization assignment for each participant at that time. **NCORP coordinators will know the randomization assignments; however participants are not to be notified of their randomization assignments until they have completed all baseline assessments.** The participants randomized to each of the three conditions will all participate in the intervention they are assigned together as a group and the sessions will only contain study participants. (Note: The URCC has successfully used this method of randomization in previous studies including U3905 (the prior yoga study), U2991 and U9994 where cohorts were randomized to treatments delivered using group formats.) Participant cohorts will be recruited at each NCORP and then randomized; this will allow for statistical analyses by site.

- 5.6 A total enrollment of 720 participants (accounting for 30% of participants providing non-evaluable data) is planned as follows:

Group	N	Evaluable
YOCAS	240	168
CBT-I	240	168
Health Education	240	168

- 5.7 Randomization will be stratified by ISI severity score obtained during the screening process (ISI score of 10-18 = “moderate” and 19-28 = “severe”) and hormone therapy (two levels: yes/no). In addition, participant cohorts will be recruited at each NCORP and then randomized; this will, in turn, allow for statistical analyses by site.
- 5.8 The three study arms are as follows:
- Arm 1 = The standard YOCAS® intervention  

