Each assessment will include 1) questionnaires on sleep (ISI, PSQI, MEQ-SA), mood (POMS), anxiety (STAI), depression (CES-D), pain (BPI and VAS), fatigue (MFSI, BFI, FACIT-F), cognitive problems (FACIT-COG), exercise (Godin), symptoms (Symptom Inventory), sleep medications and stimulant use (medication and CAM Use forms), and quality of life (FACIT), 2) a daily diary for assessing sleep patterns and specific symptoms, 3) one week of actigraphy 4) physical function tests (6-minute walk and handgrip tests), 5) and a fasting blood draw. The actigraphs are small, water-resistant devices; one is worn around the wrist for 7 consecutive days to gather data on sleep and circadian rhythm. The other is worn on the waist for the same 7 consecutive days to determine physical activity. Participants will complete their questionnaires at the time of their assessments or at home.

- 6.14 **Requesting Actigraphs, Blood Draw Kits and Other Study Materials:** Study initiation materials will be shipped to the NCORP after the entire cohort is registered. These materials are comprised of 1) the coordinator's kit (including equipment for conducting the 6-minute walk test and handgrip test), 2) the video recorder, 3) actigraphs, 4) yoga kits, and 5) blood supplies. The study supplies will be shipped from the Research Base via FedEx for delivery within 2-3 business days.
- 6.15 **Baseline Assessments:** Baseline assessments will occur on Study Days -7 to -1, or during study week 1. The coordinator will charge and initialize the actigraphs. The actigraphs should be initialized no earlier than the Wednesday prior to baseline week to ensure adequate data storage. The coordinator will also instruct all participants on how to put each actigraph on and give them written instructions. An actigraph manual along with videos and training sessions are provided for coordinators by the Research Base. The coordinator will reinforce with the participant to wear their actigraphs for 7 consecutive days and to begin filling out their daily diaries on day -7. Only NCORP site staff who have completed the URCC YOCAS® study actigraphy training can instruct participants on how to wear them and give them to participants.

All participants will be asked to complete on study data and clinical information forms as well as a series of questionnaires to evaluate insomnia, their emotional state, and their physical health. The questionnaires will take

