Hypothesis 2 = YOCAS® vs. health education). **The response will be post-treatment ISI total score.** The model fixed effects will be Group and Baseline ISI. NCORP Site will be included as a random effect. The REML method will be used to estimate the random effect variance components. If the NCORP Site variance component is significant, the fixed effects will be tested using F tests with the Kenward-Roger degrees of freedom adjustment. If the NCORP Site variance component is not statistically significant, we will use ordinary least-squares estimation and F-Tests for testing the fixed effects. The mean difference between groups with associated 95% confidence intervals will be estimated using the appropriate contrasts. An alpha level of 0.025 will be used to adjust for multiple comparisons. Additional follow-up analyses will include NCORP site and cohort as covariates and examine possible interactions.

- 10.7.2 **Secondary Aim 2 Analyses:** To examine if YOCAS® is effective for improving **objective symptoms of insomnia** (sleep latency, sleep efficiency, wake after sleep onset, sleep duration, and daytime napping via actigraphy) and **global sleep quality impairment** (PSQI total) compared to CBT-I and a health education control, we will use the same methods as for Primary Aim 1 with no multiple comparison adjustments.

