## 11.0 Records To Be Kept

Measure	Screening	Baseline	Mid-Point Intervention	Post-Intervention	3 Month Follow-Up	6 Month Follow-Up
Eligibility and Consent		✓				
DSM-V	✓					
Insomnia Severity Index Screening	✓					
On-Study Data/Participant Interview		✓				
Clinical Record Information		✓				
Cancer Treatment Notes		✓				
Sleep Medication and CAM Use		✓	✓	✓	✓	✓
Stimulant Medication and CAM Use		✓	✓	✓	✓	✓
Insomnia Severity Index (ISI)		✓	✓	✓	✓	✓
Sleep Quality (PSQI)		✓	✓	✓	✓	✓
Sleep Chronotype (MEQ-SA)		✓	✓	✓	✓	✓
Actigraphy		✓	✓	✓	✓	✓
6-Minute Walk Test		✓	✓	✓	✓	✓
Handgrip Dynamometer Test		✓	✓	✓	✓	✓
Fasting Blood Draw (Blood Requisition Form)		✓	✓	✓	✓	✓
Symptom Inventory (SI)		✓	✓	✓	✓	✓
Fatigue Interference (BFI)		✓	✓	✓	✓	✓
Cancer-Related Fatigue (FACIT-F)		✓	✓	✓	✓	✓
Cancer-Related Fatigue (MFSI)		✓	✓	✓	✓	✓
Depression Symptoms (CES-D)		✓	✓	✓	✓	✓
Anxiety (STAI)		✓	✓	✓	✓	✓
Mood (POMS)		✓	✓	✓	✓	✓
Cognitive Problems (FACIT-COG)		✓	✓	✓	✓	✓
Quality of Life (FACIT)		✓	✓	✓	✓	✓
Pain (BPI)		✓	✓	✓	✓	✓
Pain (VAS)		✓	✓	✓	✓	✓
Leisure Time Physical Activity (GODIN)		✓	✓	✓	✓	✓
Daily Diary		✓	✓	✓	✓	✓
Feedback Questionnaire						✓
Qualitative Exit Interview						✓

Call Log		✓✓ 	✓	✓	✓	✓
Attendance Log				✓		

A second phone call is made at the end of baseline.

- 11.1 All written materials will be kept confidential, locked in the file room at the Research Base that is accessible only by Research Base personnel, and identified by study ID numbers. Electronic databases are password-protected with limited access.
- 11.2 Any treatment notes related to the study participant’s cancer treatment should be submitted with the baseline assessment.
- 11.3 The Case Summary should accompany ALL data submissions. Completed forms must be electronically submitted through the URCC Box upload system within 30 days of assessment time point
- 11.4 All electronic data collected, i.e., actigraphy files and video recordings must be stored on a HIPAA compliant, regularly backed up network storage or computer immediately after collection until notified by URCC to destroy it.

---

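### The primary ANCOVA leaves out both randomisation stratifiers, screening ISI and hormone therapy; pre-specifying them costs almost nothing and may narrow both primary intervals by roughly 0% to 7%.

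*Combined protocol and SAP*

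**What the plan says.** Section 5.7 states: "Randomization will be stratified by ISI severity score obtained during the screening process", in two bands (10-18 and 19-28), together with hormone therapy (yes/no). Section 5.3.5.1 makes the screening score a condition of registration ("Documentation of eligibility screening score of" at least 10), and 5.3.7.8 asks for both stratifiers at registration. The table in section 11.0 lists "Insomnia Severity Index Screening" on its own row, separate from the ISI at baseline and later visits.

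The baseline ISI comes later. Section 6.15 says "Baseline assessments will occur on Study Days -7 to -1, or during study week 1", and under 5.5 a cohort is registered and randomised once all its members have consented.

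For the primary analysis, section 10.7.1 takes post-treatment ISI as the response and says "The model fixed effects will be Group and Baseline ISI" and "NCORP Site will be included as a random effect". It then adds: "Additional follow-up analyses will include NCORP site and cohort as covariates and examine possible interactions". Neither stratifier appears in the primary model or is named in those follow-up analyses. Section 10.6.2 plans multiple imputation under MAR without naming the imputation variables.

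**The concern.** The ISI is measured twice before treatment, and the primary analysis uses only the second reading. A single self-report score is a noisy measure of usual severity, so two readings may predict the post-treatment score better than one. Any prognostic information in the screening score or hormone status that baseline ISI does not carry stays in the error term, although randomisation was balanced on these factors.

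At stake is precision in both primary comparisons. Hypothesis 1 (non-inferiority to CBT-I) is planned at 80% power with no reserve. The two stratifiers should also be complete for everyone randomised, which makes them natural imputation predictors in a plan that allows for 30% without complete data.

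**Working it through.** **Inputs from the documents (10.1, 10.2.1, 10.7.1).** ISI SD 4.6; baseline-post correlation a = 0.576; 168 evaluable per arm; margin 1.15; alpha 0.025, one-sided for Hypothesis 1.

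**Assumed inputs.** b = screening-post correlation, 0.45 to 0.576; r = screening-baseline correlation, 0.6 to 0.9. The documents give neither.

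**Step 1: the plan's own figure.**
- Residual SD = 4.6 × √(1 − 0.576²) = 3.760.
- SE of the difference = 3.760 × √(2/168) = 0.410.
- Power = Φ(1.15/0.410 − 1.96) = 80.0%, and n for 80% power is 168 per arm. The stated figure reproduces with baseline ISI as the only covariate.
- Hypothesis 2 at two-sided 0.025 gives detectable differences of 1.26, 1.45 and 1.59 at 80%, 90% and 95% power, consistent with the plan's 1.3, 1.5 and 1.6.

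**Step 2: add the continuous screening score.**
- R² = (a² + b² − 2abr)/(1 − r²), compared with a² = 0.332 for baseline alone.
- Fall in residual variance = (R² − a²)/(1 − a²).
- Relative interval width = √(1 − fall).

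Example, b = 0.576 and r = 0.7: R² = (0.3318 + 0.3318 − 0.4645)/0.51 = 0.390. The fall is (0.390 − 0.332)/0.668 = 8.8%, so the interval is 4.5% narrower.

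| b | r | Residual variance falls | Interval narrower | H1 power |
|---|---|---|---|---|
| 0.576 | 0.6 | 12.4% | 6.4% | 85.0% |
| 0.576 | 0.7 | 8.8% | 4.5% | 83.5% |
| 0.576 | 0.8 | 5.5% | 2.8% | 82.2% |
| 0.576 | 0.9 | 2.6% | 1.3% | 81.1% |
| 0.50 | 0.6 | 5.6% | 2.8% | 82.2% |
| 0.50 | 0.7 | 2.7% | 1.4% | 81.1% |
| 0.50 | 0.8 | 0.6% | 0.3% | 80.3% |
| 0.50 | 0.9 | 0.3% | 0.1% | 80.1% |
| 0.45 | 0.6 | 2.6% | 1.3% | 81.0% |
| 0.45 | 0.7 | 0.6% | 0.3% | 80.3% |
| 0.45 | 0.8 | 0.05% | 0.02% | 80.1% |

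At b = 0.45 and r = 0.9 the formula gives 1.9%, but only through a negative coefficient for the screening score, which is implausible for a second reading of the same scale. At b = 0.576 the sample size for 80% power falls from 168 to between 164 (r = 0.9) and 148 (r = 0.6) per arm. Both comparisons use the same SE formula, so both intervals shrink in the same proportion.

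**Step 3: allow for the entry cut-off.** A simulation of two equally reliable ISI scores, with entry at screening ISI of 10 or more and reliability from 0.9 down to 0.6, gives intervals 2.1% to 6.8% narrower with the continuous score (H1 power 81.7% to 85.3%). Using only the two-level band gives 0.7% to 3.8%. The 6.8% figure is the source of the upper limit of about 7%; truncation had reduced the screening-baseline correlation there to 0.49.

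**Step 4: worst case.** If the screening score adds nothing beyond baseline (b = r × 0.576), the only cost is one degree of freedom: √(331/330) = 1.0015, an interval about 0.15% wider. Hormone therapy costs the same again if it too adds nothing. The break-even partial R² is about 1/332 = 0.3% per covariate.

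**The case against.** The strongest objection is that nothing here is wrong. ANCOVA on the post-treatment score with its baseline is a standard, valid primary model, and the stated power needs no second covariate. That stands. A reader might infer from the omission that the primary test is invalid or the trial underpowered; the reproduced 80% contradicts the second inference, and nothing in the documents supports the first.

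The second objection is that the gain may be negligible. Screening ISI is the older reading, taken before a cohort of 15 to 30 is assembled, possibly from a telephone approach (6.11), and cut off at 10 by eligibility. It may therefore predict the post-treatment score less well than baseline does. That also stands. It is tempting to say that the extra covariate will certainly narrow both intervals at no cost, but this requires the score to predict outcome beyond baseline ISI, and the documents contain no figure for that.

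Third, someone might extend the covariate to the 3- and 6-month analysis (10.7.3). That model has ISI at all five time points as the response and tests Time by Group. With complete data, a time-constant main effect cancels from those contrasts, so nothing is gained there.

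Fourth, a reader might infer that the baseline ISI is contaminated because assignments exist before the baseline week. Section 5.5 says "participants are not to be notified of their randomization assignments until they have completed all baseline assessments", so the documents do not establish this. Adding the screening score would not cure such a problem anyway.

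**Conclusion.** The point holds as a nearly free improvement in precision. Both stratifiers are known before assignment, are required at registration and are absent from the primary model. Under the assumed correlations, screening ISI narrows both primary intervals by roughly 0% to 7% and moves Hypothesis 1 power from 80% to about 80% to 85%. The upper end requires the screening score to be about as prognostic as baseline while correlating only about 0.5 to 0.6 with it. The gain from hormone therapy cannot be sized, since the documents give no association with ISI; it belongs in the model because matching the analysis to the randomisation requires both stratifiers. Baseline ISI already carries part of the severity stratifier.

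**What to change.** In 10.7.1, pre-specify the continuous screening ISI and hormone therapy (yes/no) as fixed covariates beside Group and Baseline ISI, keeping site as planned. Use the continuous score in preference to the two-level band. In 10.6.2, name both variables in the imputation model; that step, and not the extra covariate, is what helps when a baseline ISI is missing. Leave the longitudinal model in 10.7.3 as it is on this point.

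The cost is two lines of SAP text and two degrees of freedom, with no new data collection. The change should be made before any unblinded outcome data are seen, because a covariate chosen afterwards would not be credible.

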## 10.0 Data Handling and Statistical Considerations

---

- 10.1 **Sample Size and Statistical Power:** Allowing for 30% of participants who may not provide complete data (as in our prior study), we will need to enroll a total of 720 participants to have 504 fully evaluable participants (168 evaluable in each of the three study arms). Fully evaluable participants is defined as having completed the On Study/ Participant Interview and the Clinical Record Information (baseline), the ISI, PSQI, Daily Diaries, and actigraphy (baseline and post-intervention assessments) for primary and secondary endpoints. With 504 fully evaluable participants, will have 80% power at a 0.025 significance level to test our hypotheses. We will use a significance level of 0.025 to control for type I error because two hypotheses (i.e., 1 inferiority [yoga vs. CBT-I] and 1 superiority [yoga vs. health education]) will be tested in our primary aim. *[Note: We will reimburse survivors for participating in this study in an effort to decrease attrition and data loss.]*
- 10.2 **Power for Primary Aim 1:** The two primary hypotheses to be tested in our primary aim include: (1) YOCAS® will be as effective as CBT-I, and (2) YOCAS® will be more effective than the health education control.
- 10.2.1 **Power for Hypothesis 1:** Based on baseline data from our previous phase III RCT examining the effects of yoga on insomnia and data from Savard and Morin, we assume an ISI standard deviation of 4.6. Since half a standard deviation is commonly accepted as appropriate for estimating a clinically important change, we regard a difference of 2.3 (half a standard deviation) between YOCAS® and CBT-I as nontrivial. Following the same methods as Garland and colleagues, we set the non-inferiority margin to 1.15 (half of the 2.3 difference). We will test the **null** hypothesis that the difference in mean change on the ISI between YOCAS® and CBT-I is greater than 1.15; that is, YOCAS® is *inferior* to CBT-I. Rejection of the null hypothesis means that YOCAS® is as effective (*non-inferior*) as CBT-I. Using ANCOVA to estimate differences in mean change between YOCAS® and CBT-I, a correlation of 0.576 (from our prior study), and a sample of 168 subjects per group, we will have sufficient (80%) power to detect non-inferiority using a margin of 1.15 at  $p = 0.025$ .

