- 10.6 Unless otherwise stated, all statistical tests will be performed at the two-tailed 5% level of significance. Likewise, 95% confidence intervals will be constructed for estimation of effects (e.g., difference in mean CRF, aerobic capacity, strength and QOL between the active treatment group and the control group). Data will be analyzed on an "intent-to-treat" basis; participant data will be included in the treatment group to which the participant was randomized, regardless of any subsequent changes to the treatment (treatment in this study is considered the study intervention, i.e., exercise intervention, CBT-I, or Health education standard care).
- 10.6.1 **Assumptions.** The assumptions underlying all statistical analyses will be thoroughly checked using appropriate graphical and numerical methods. For the ANCOVA analyses, the assumptions are bivariate normality of the Pre- and Post-treatment responses with common covariance matrices, after correction for the model fixed effects. Bivariate normality will be assessed with Roysten's procedure, and equality of the covariance matrices will be assessed with the Box M test. The ISI data from our previous trial did not show violations of these assumptions. If distributions are markedly skewed, we will apply transformations as appropriate. The biomarker data will likely require a logarithmic transformation, as is common practice. If heteroscedistic variance is found in the residuals for any of the models, a Box-Cox transformation will be applied to the data. As a last resort, appropriate nonparametric methods will be attempted, e.g. Wilcoxon rank sum test on change scores. If outliers or influential data are detected, the accuracy of the data will be investigated. If no errors are found, analyses may be repeated after removing these cases to evaluate their impact on the results. However, the final analyses will include these data points.

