- 10.6.2 **Missing Values.** Every effort will be made to facilitate participants' completion of questionnaires and provision of actigraphy and physical function data, and blood. In the event of missing data, the reasons for missing data will be recorded and tabulated according to treatment group. Some missing data are inevitable. Under the missing at random (MAR) assumption, we will use multiple imputation to obtain unbiased estimates of key parameters. If data are suspected to be missing not at random (MNAR), a sensitivity analysis using the methods of Liublinska and Rubin (2014) will be run to determine the impact on results. If the estimates are similar to the ones obtained from the simpler analysis of only complete cases, we will report the complete-case analysis results.
- 10.7 **Statistical Analyses:**
- 10.7.1 **Primary Aim 1 Analyses:** To determine if YOCAS® is as effective as CBT-I and more effective than health education for improving **insomnia (ISI total)**, two separate analyses will be performed, each aimed at estimating the difference between arms in mean change from baseline with associated confidence intervals. The comparison of YOCAS® to CBT-I is a non-inferiority hypothesis with a one-sided alpha, and the comparison of YOCAS® to the health education control is a traditional null hypothesis of no difference with a two-sided alpha. See the Statistical Power section for more details. A linear mixed effects ANCOVA will be used to assess the statistical significance of the differences in mean changes from baseline for the two groups (Hypothesis 1 = YOCAS® vs. CBT-I;

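### The YOCAS versus health education contrast is tested two-sided at 0.025 but reported with a 95% confidence interval, so the interval can exclude zero when the planned test fails

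*Combined protocol and SAP*

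**What the plan says.** Section 10.1 sets the level for the primary aim: "We will use a significance level of 0.025 to control for type I error because two hypotheses" are tested there, one of non-inferiority and one of superiority. Section 10.7.1 repeats it: "An alpha level of 0.025 will be used to adjust for multiple comparisons".

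Section 10.7.1 also gives the sidedness. The comparison of YOCAS with CBT-I (Hypothesis 1) "is a non-inferiority hypothesis with a one-sided alpha"; the comparison of YOCAS "to the health education control is a traditional null hypothesis of no difference with a two-sided alpha" (Hypothesis 2).

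For reporting, the same section has one sentence covering both contrasts: "The mean difference between groups with associated 95% confidence intervals will be estimated using the appropriate contrasts". It gives no separate level for Hypothesis 2.

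The general rule is in Section 10.6: "Unless otherwise stated, all statistical tests will be performed at the two-tailed 5% level of significance". That section then sets 95% intervals for estimating effects, as the companion to the 5% tests.

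**The concern.** Section 10.6 pairs a 5% two-sided test with a 95% interval. Section 10.7.1 lowers the test level to 0.025 for the primary comparisons but leaves the interval at 95%. For Hypothesis 1 this does no harm, because a two-sided 95% interval is the counterpart of a one-sided 0.025 test. For Hypothesis 2 the matching interval is 97.5%. One interval level thus serves two tests that need different levels.

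The interval will carry weight with readers. Section 10.7.1 describes both primary analyses as estimating the between-arm difference with its confidence interval. An F test of the group effect does not by itself test a 1.15 margin, so for Hypothesis 1 the interval is the natural thing to read, and many will read Hypothesis 2 in the same way. If the estimate falls in the gap between the two levels, the primary superiority result would show an interval clear of zero beside a p-value that misses its threshold, and the plan does not say how to report that.

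**Working it through.** **Inputs.** ISI standard deviation: "we assume an ISI standard deviation of 4.6" (Section 10.2.1). Baseline-to-post correlation 0.576 and 168 evaluable per arm (Sections 10.2.1 and 10.2.2). Non-inferiority margin 1.15 (Section 10.2.1).

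**Step 1: standard error.** For ANCOVA, the adjusted SD = 4.6 × √(1 − 0.576²) = 3.760. SE of a two-arm difference = 3.760 × √(2/168) = 0.410.

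**Step 2: reproduce the plan's figures, to settle which 0.025 is meant.** The two-sided statement and the 0.025 stand in different sentences, so 0.025 could in principle mean 0.025 per tail, which would make 95% correct. Detectable difference = (critical value + z for power) × SE:

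| Test level for Hypothesis 2 | 80% power | 90% power | 95% power |
|---|---|---|---|
| Stated in Section 10.2.2 | 1.3 | 1.5 | 1.6 |
| Two-sided 0.025, normal (critical value 2.241) | 1.265 | 1.445 | 1.594 |
| Two-sided 0.025, t with 333 df | 1.270 | 1.451 | 1.600 |
| Two-sided 0.05, i.e. 0.025 per tail, normal (1.960) | 1.15 | 1.33 | 1.48 |

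The t-based row at two-sided 0.025 rounds to the stated figures. The per-tail reading gives none of them. The planned test of Hypothesis 2 is therefore two-sided 0.025.

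For Hypothesis 1, a margin of 1.15, one-sided 0.025 and 80% power require 168 per arm, as stated.

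**Step 3: interval half-widths.**
- 95%: 1.960 × 0.410 = 0.804 (0.807 with t).
- 97.5%: 2.241 × 0.410 = 0.920 (0.924 with t).
- Ratio: 2.241 / 1.960 = 1.14.

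**Step 4: the zone of conflict.** An absolute estimate between 0.804 and 0.920 has a two-sided p between 0.025 and 0.05. For example, an estimate of 0.86 has a 95% interval of 0.06 to 1.66, a 97.5% interval of −0.06 to 1.78, and p = 0.036.

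**Step 5: how often it would happen.** Probability that the estimate falls in the zone, in either direction (normal approximation, SE 0.410):

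| True difference (ISI points) | Probability |
|---|---|
| 0 | 2.5% |
| 0.86 (centre of the zone, the maximum) | about 11% |
| 1.15 | 8.8% |
| 1.27 (80% power) | 6.9% |
| 1.3 | 6.4% |
| 1.6 | 2.2% |

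The maximum follows from the width of the zone: (0.920 − 0.804) / 0.410 = 0.28 standard errors, and a normal distribution centred on it puts about 11% there.

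**The case against.** The strongest reply is that the plan does not use the interval to decide superiority. Section 10.7.1 uses the ANCOVA to assess significance; where site variance matters, "the fixed effects will be tested using F tests with the Kenward-Roger degrees of freedom adjustment", and otherwise ordinary least-squares F tests apply. The 0.025 level comes in the sentence right after the interval, and Section 10.6 describes 95% intervals as serving estimation. An unadjusted 95% interval beside a multiplicity-adjusted test is coherent if it is labelled as such. The zone is also narrow, and every estimate in it lies below the 1.15 margin and well below the 2.3 points that Section 10.2.1 calls nontrivial.

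Most of this stands. It means that the test governs, and it limits the practical consequence. It does not remove the mismatch: the plan attaches no descriptive label to the interval and departs from its own pairing in Section 10.6 without saying why.

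Two stronger readings are tempting, and the documents support neither. A reader might infer that the 95% interval defeats the multiplicity control, adding 2.5% for Hypothesis 1 to 5% for Hypothesis 2 to reach 7.5%. That needs a rule under which the 95% interval decides Hypothesis 2, and no section states one. Even under that rule, only one tail of Hypothesis 2 would wrongly favour YOCAS, so false claims in its favour would total at most 2.5% + 2.5% = 5%. A reader might also infer that 95% is wrong for both primary contrasts; for Hypothesis 1 it is right.

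**Conclusion.** The point holds as a mismatch between the stated interval level and the stated test for one primary contrast, YOCAS versus health education. It is not an inflation of type I error: with the 0.025 test deciding, the error for Hypothesis 2 stays at two-sided 2.5%. It would rise to two-sided 5% only if the 95% interval were read as the decision rule.

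The size of the zone rests on the plan's SD, correlation and 168 evaluable per arm, and takes no account of the site effect or imputation. With another standard error the limits move in proportion (1.96 to 2.24 standard errors), but the conflict always covers p-values between 0.025 and 0.05. It is worth correcting before results are seen, because the plan would otherwise leave a choice between two readings of its primary superiority result.

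**What to change.** In Section 10.7.1, replace the single interval sentence with one statement for each hypothesis:

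- **YOCAS versus health education:** report a two-sided 97.5% confidence interval, and state that superiority is judged at two-sided p < 0.025. If a 95% interval is also shown for this contrast, label it descriptive.
- **YOCAS versus CBT-I:** keep the two-sided 95% interval, read against the 1.15 margin.

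Confine the 97.5% level to Hypothesis 2. Section 10.7.2 borrows the primary methods for the secondary outcomes without multiplicity adjustment, so 95% remains consistent there.

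The cost is a short wording change and a Hypothesis 2 interval about 14% wider. The estimate, the planned test, the sample size and the power are unchanged.
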